# 6.6 Concurrent Medications

Patients may NOT be treated concurrently with therapeutic dosing of antifibrinolytics, or anticoagulants, including (but not limited to) therapeutic dosing with heparin, systemic t-PA, or warfarin. The use of non-therapeutic doses of heparin ( $\leq 7,500$  units Q8Hours) or low molecular weight heparin ( $\leq 1$  mg/kg/day) is allowed. Patients may also receive heparin or other anticoagulants for routine central venous line management, intermittent dialysis or ultrafiltration. Fibrinolytic instillation for central venous line occlusion is also permitted.

#### 6.7 Supportive care

Hematologic: Platelet transfusions should be given to maintain a platelet count ≥ 50,000/mm3 at all times, and fresh frozen plasma or cryoprecipitate given to maintain a serum fibrinogen level > 150 mg/dl during the duration of study therapy.

Infectious disease: Antimicrobial therapy for prophylaxis or treatment of acute infections should continue as clinically indicated, per investigator discretion.

Hepato-renal: There is no change in defibrotide dosing with hepatic and/or renal dysfunction. Patients receiving hemodialysis, peritoneal dialysis or ultrafiltration may continue study therapy without dosing modification.

# 7.0 REQUIRED OBSERVATIONS

For sections 7.2 through 7.4, if a laboratory parameter has been obtained within 48 hours prior to study enrollment, it does not need to be repeated for study purposes and will be considered the \*baseline\* value. Following the last day of study drug therapy, no further "study related" blood tests will be obtained.

Guidelines for monitoring hematologic and coagulation parameters were derived from Thachil, J., et al., *ISTH interim guidance on recognition and management of coagulopathy in COVID-19.* J Thromb Haemost, 2020. **18**(5): p. 1023-1026.

**7.1 Pulmonary Indices**: Pulmonary parameters will be recorded daily for subjects from the time of study entry to cessation of study drug therapy. Pulmonary assessment will include a subject's current level of supplemental oxygen support (%FiO2), current modality of support (mechanical ventilation, BiPaP, CPAP, nasal cannula, or none), and the results of any chest radiographs (if performed) that day. For patients that remain hospitalized on day 14 of study, pulmonary indices will also be made at that time point.

Blood gas values will be obtained as clinically indicated. Scoring from the WHO COVID Ordinal Scale (Appendix 1) will be determined daily by study investigators, till cessation of study drug therapy.

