# 3.2 Secondary Objectives

To assess the therapeutic response of defibrotide therapy for patients with SARS-CoV2 related ARDS, including: Day 14, ventilator free survival.

- a. The number of ventilator free days within 14 days of study entry.
- b. The time to improvement in oxygenation, with improvement in oxygenation defined as an increase in PaO2/FiO2 of 50 (or greater) compared to the nadir of PaO2/FiO2.
- c. To use the "WHO COVID-19 Ordinal Scale" to assess the mean change in the WHO scores during study therapy.
- d. Overall Survival at 28 days.

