# 6.3 Therapy duration

The planned duration of study therapy is 7 days (168 hours) from study entry, with the following qualifications:

- a. Patients who respond to study therapy prior to the 7-day period, as evidenced by a decline in the WHO Ordinal Score by  $\geq$  2 points (APPENDIX 1) for > 48 consecutive hours, may discontinue study therapy at that earlier time point.
- b. Patients who have not responded to study therapy by day 7 of therapy, evidenced by <20% reduction (or a worsening) of the amount of supplemental oxygen they are receiving, will discontinue study therapy at that time point (day 7).
- c. Patients who have evidence of a partial pulmonary response by day 7 ( $\geq$ 20% reduction in supplemental O2 requirement, but still require supplemental oxygen) may elect to continue to receive study drug through an additional 7 days of study (total 14-day therapy course).

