# 15.0 APPENDIX 1: WHO Ordinal scale to assess clinical improvement

Patient State	Descriptor	Score
Ambulatory	No limitation of activities	1
	Limitations of activities	2
Hospitalized	No oxygen therapy	3
(mild disease)	Oxygen by mask or nasal prongs	4
Hospitalized	Non-invasive ventilation or high-flow oxygen	5
(severe disease)	Intubation and mechanical ventilation	6
	Mechanical ventilation + additional organ support -	7
	pressors, RRT, ECMO	
Dead	Death	8

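### The WHO-scale objective (3.2c) is scored only while drug is given, so its mean change is taken over windows whose length depends on each patient's course

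*Combined protocol and SAP*

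**What the plan says.** Section 3.2, item c, uses the WHO COVID-19 scale "to assess the mean change in the WHO scores during study therapy". It names no read-out day. Section 7.1 has the matching collection rule: the score "will be determined daily by study investigators, till cessation of study drug therapy". No WHO score is scheduled later. The Day 14 assessment in 7.1 and in note e of the 7.7 schedule covers pulmonary indices only, and only for inpatients. The 7.7 table has no WHO-score row.

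Section 6.3 plans 7 days of therapy with three qualifications:

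- (a) A patient whose WHO score has fallen by at least 2 "points (APPENDIX 1) for > 48 consecutive hours, may discontinue study therapy at that earlier time point".
- (b) A patient with less than a 20% reduction in supplemental oxygen stops at Day 7.
- (c) A partial responder who still needs oxygen may continue to Day 14.

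Section 6.4 adds permanent stops for bleeding that recurs after a restart, CNS or diffuse alveolar hemorrhage, severe hypersensitivity, and ECMO.

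Appendix 1 assigns 1 and 2 to ambulatory patients, 3 to 7 to hospitalized patients and 8 to death. Section 8.4 gives an analysis for two binary Day 14 endpoints and none for the WHO score.

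**The concern.** A change score is interpretable when everyone is read at the same time from the same origin. Here the reading ends when drug ends, and drug ends for reasons tied to the outcome. Under 6.3(a) the WHO scale can close its own measurement window, and it does so at a favourable value. Partial responders can be observed for twice as long as non-responders. Patients who bleed repeatedly, bleed at a critical site or go onto ECMO leave the window when that happens.

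What follows the last dose is not scored, whether relapse, death or recovery to discharge. The resulting mean is hard to read as a response measure and is not comparable with results taken on a fixed day. This matters because 3.2 lists it under therapeutic response, and section 2.0 presents the trial as the foundation for a phase 2 study.

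**Working it through.** The documents give no effect size, standard deviation or target for this objective, so there is no stated figure to reproduce. The check is to compare the sections and then size the effect.

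**Length of the scoring window, from 6.3, 6.4 and 7.1**

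| Course | Last WHO score |
|---|---|
| WHO fall of at least 2 points held over 48 hours, drug stopped (optional) | before Day 7 |
| Non-response | Day 7 |
| Partial response, extended (optional) | up to Day 14 |
| Recurrent bleeding, CNS or diffuse alveolar hemorrhage, severe hypersensitivity, ECMO | day of permanent stop |
| Death on drug | day of death, can be scored 8 |

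**Scores out of reach.** Section 6.2 gives drug as 2-hour infusions about every 6 hours. Scores 1 and 2 are therefore in practice unreachable while scoring runs. This is an inference; no sentence says so. A patient entering at 4 ("Oxygen by mask or nasal prongs"), eligible through supplemental oxygen under 5.1.4(b), can then fall by at most 4 − 3 = 1 point, below the 2 points named in 6.3(a).

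**Effect of one unscored event.** Take the change as last on-drug score minus baseline, which is an assumption because 3.2c does not define it. With n = 12 (section 8.2), the shift in the mean is (later score − score at drug stop) / 12.

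| Score at drug stop | Later death (8) | Later discharge at 2 | Later discharge at 1 |
|---|---|---|---|
| 3 | +5/12 = +0.417 | −1/12 = −0.083 | −2/12 = −0.167 |
| 4 | +4/12 = +0.333 | −2/12 = −0.167 | −3/12 = −0.250 |
| 5 | +3/12 = +0.250 | | |
| 6 | +2/12 = +0.167 | | |
| 7 | +1/12 = +0.083 | | |

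A positive shift means the true mean is worse than the recorded one. Omitted deaths flatter the result and omitted discharges understate it. One death from score 6 (+0.167) is cancelled by one discharge from 4 to 2 (−0.167), so the sign of the net bias depends on the case mix.

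**An assumed cohort of 12** (invented to show scale, not taken from the documents)

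| Patients | Baseline | At drug stop | Day 14 | Sum of changes at stop | Sum of changes at Day 14 |
|---|---|---|---|---|---|
| 3 early responders | 5 | 3 | 2 | −6 | −9 |
| 2 partial responders | 6 | 5 | 5 | −2 | −2 |
| 3 non-responders who die later | 6 | 6 | 8 | 0 | +6 |
| 2 non-responders, stable | 6 | 6 | 6 | 0 | 0 |
| 1 permanent stop for bleeding | 5 | 5 | 6 | 0 | +1 |
| 1 death on drug | 6 | 8 | 8 | +2 | +2 |

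Mean at drug stop: −6/12 = −0.50, read on days 3 to 14. Mean at fixed Day 14: −2/12 = −0.17. In this example the recorded mean overstates improvement by 0.33 points without changing sign.

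**The case against.** The strongest reply is that 3.2c and 7.1 agree. The objective is stated as an on-therapy change and is collected that way, so there is no contradiction. That stands: this is a weakness of endpoint definition. It is also one descriptive item in a 12-patient study whose primary endpoint is hemorrhage, and no decision rests on it.

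Several further points also stand:

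- Late deaths are not lost to the trial. Day 14 survival and Day 14 ventilator-free survival (8.4), 28-day survival (3.2d) and the 30-day contact (7.7, note h) all capture them.
- Most bleeds cause a hold with possible resumption, so a bleed does not by itself end scoring. The protocol does not say whether scoring continues during a hold.
- Day 7 is the planned end of therapy, so the non-response stop is not early. The stop in 6.3(a) is optional.
- Part of a Day 14 score could be rebuilt from vital status and inpatient support modality. The indices in 7.1 do not record the organ support that separates 6 from 7, and nothing is planned for discharged patients.
- The wording of 3.2c could also mean an average over daily scores. That would change the arithmetic but not the dependence on when drug stops.

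A reader might go further and infer that the design is biased towards benefit, or that it can turn worsening into apparent improvement. Three chosen patients can show this: recorded changes −1, −2 and 0 (mean −1.0) against Day 14 changes −2, +3 and +2 (mean +1.0). The documents do not support that as an expectation. Two of the three are assumed to die after stopping. The first is assumed to improve from 4 to 3 and leave on Day 5, an early stop for which 6.3 gives no basis. Dropping only the second gives a Day 14 mean of (−2 + 2)/2 = 0, so the worsening disappears.

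**Conclusion.** The point holds as a design weakness of a secondary objective. Followed exactly, the plan yields a mean change over periods of under 7, 7 or up to 14 days, with the period set by the patient's course and in one case by the WHO score itself. Relapse and death after the last dose are omitted from the score. So, in practice, are discharge scores, on the inference that dosing every 6 hours keeps patients in hospital.

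The size is about 0.08 to 0.42 points of the 12-patient mean per unscored later death or discharge, assuming the last on-drug score is the one analysed. The net direction is not fixed, and neither a consistent bias towards benefit nor a sign reversal should be claimed. The primary safety endpoint and the survival endpoints are unaffected. The change is worth making because scores for discharged patients may be unrecoverable later.

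**What to change.** 1. **3.2c:** define the endpoint as change in WHO score from baseline to Day 7 and to Day 14 after first dose, in all patients given at least one dose, whether or not still on drug, with death scored 8.
2. **7.1:** continue WHO scoring through Day 14 regardless of drug status. This also settles scoring during a hold.
3. **7.7:** add a WHO-score row. Editing note e would not do, because it covers pulmonary indices only. Patients discharged before Day 14 are scored from the record or by a brief Day 14 call.
4. **8.4:** state the summary, for example the mean change with the number of patients at each score on Day 7 and Day 14.

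The treatment rules in 6.3 and 6.4 need no change. The on-drug daily scores can still be listed if an on-therapy description is wanted.

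The cost is protocol wording, chart review after drug stops, and a short call for those discharged, in at most 12 patients. Section 8.4 already needs vital and ventilator status at Day 14 for every patient, and the synopsis already foresees 14 days of monitoring, so little new collection is involved.

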#### 7.2 Hematologic parameters:

A complete blood count including platelets (CBCP) should be obtained at baseline (study entry), and daily till cessation of study therapy. Additional blood counts may be obtained as clinically indicated.

#### 7.3 Chemistries:

Serum chemistries (Electrolytes, BUN, creatinine, liver panel) should be obtained at baseline (study entry), and upon cessation of study therapy. Additional chemistries should be obtained as clinically indicated.

#### 7.4 Coagulation Labs:

D-dimer, Prothrombin time (PT), and serum fibrinogen should be obtained at baseline (study entry) and daily till cessation of study therapy. Additional D-dimer, PT, and serum fibrinogen testing may be obtained as clinically indicated.

#### 7.5 Serologic Cytokine Profiles:

Approximately 3-5 ml of plasma will be drawn at baseline (±1 day), day 4 (±2 days), day 7 (±2 days), and upon completion of study therapy (±2 days) for cytokine analysis. For subjects completing study therapy prior to day 7, samples will be acquired upon completion of study therapy (±2 days), without a day 7 sample acquired. For subjects completing study therapy after day 7, an additional sample will be acquired upon completion of study therapy (±2 days). The inability to obtain these ancillary tests on the specified days will not be considered a protocol violation.

# 7.6 Biomarkers of hemostasis and endothelial dysfunction:

Biomarkers of hemostasis and endothelial dysfunction will be obtained from the 3-5 ml of plasma as described in section 7.5. Serologic biomarkers of hemostasis and endothelial dysfunction may include (but are not limited to): PAI-1, Protein C, tPA, VWF. The inability to obtain these ancillary tests on the specified days will not be considered a protocol violation.

For subjects completing study therapy prior to day 7, samples will be acquired upon completion of study therapy (±2 days), without a day 7 sample acquired. For subjects completing study therapy on day 7, samples will be acquired at baseline, day 4 (±2 days) and day 7 (±2 days) of therapy. For subjects completing study therapy after day 7, samples will be acquired at baseline, day 4 (±2 days), day 7 (±2 days), and upon completion of study therapy (±2 days).

# 7.7 Study Schedule of Events

	Baseline	Day 1	Day 2 f	Day 3 f	Day 4 f	Day 5 f	Day 6 f	Day 7 f	30 days post h
Eligibility screen	X								
Informed consent	Х								
Medical history	Xa	Х	Х	Х	Х	Х	Х	Х	
Physical exam	Xa	Х	Х	Х	Х	Х	Х	Х	
CBC (platelets)	Xa	Х	Х	Х	Х	Х	Х	Х	
Chemistries	Xa							Х	
D-dimer	Xa	Х	Х	Х	Х	Х	Х	Х	
PT	Xa	Х	Х	Х	Х	Х	Х	Х	
Fibrinogen	Xa	Х	Х	Х	Х	Х	Х	Х	
ABG	Xa								
CXR	Xp								
Biomarkers c	Х				Х			Х	
Urine or serum pregnancy test d	Х								
Pulmonary Indices e	Х	Х	Х	Х	Х	Х	Х	Х	
Defibrotide		Х	Х	Х	Х	Х	Х	Х	
Vital signs g		Х	Х	Х	Х	Х	Х	Х	
Adverse Event and Follow-up h		Х	Х	Х	Х	Х	Х	Х	Х

Key: CBC-complete blood count; CXR-chest X ray; ABG-arterial blood gas; BP-blood pressure; HR-heart rate; RR-respiratory rate, Tx-treatment.

#### Notes:

- **a,** Laboratory tests performed within 48 hours prior to study entry do not need to be repeated at baseline. The D-Dimer, serum fibrinogen, PT and CBCP should be performed daily (till cessation of study drug therapy), and should be viewed as standard medical care. Arterial blood gas (ABG) measurements, and chest radiographs should be performed per routine medical care. Patients who continue therapy beyond day 7, should continue to have laboratory tests performed (as indicated above) till cessation of study therapy.
- **b**, Chest XRay (CXR): The CXR does not need to be repeated at baseline, if a CXR was done on admission and revealed bilateral infiltrates.
- **c**. Biomarkers. Five ml of plasma will be drawn at baseline (±1 day), day 4 (±1 day), day 7 (±1 day), and upon completion of study therapy (±1 day) for cytokine analysis. Patients discontinuing drug prior to day 7 are not required to have a day 7 biomarker assessment drawn."
- d. Pregnancy test: Perform in subjects of child-bearing potential, if not already performed this admission for clinical care reasons.
- **e**. Pulmonary indices will be recorded daily till cessation of drug therapy, and again at day 14 (if a patient remains hospitalized at that time). Patients who are discharged prior to day 14 do not need to have pulmonary indices assessed on day 14.
- **f.** Should be done "till "cessation of study therapy", if the defibrotide is given for a duration other than 7 days.
- **g**. Vital signs: heart rate, respiratory rate, blood pressure prior to and upon completion of the first infusion, and if clinically possible with subsequent infusions.
- **h.** Adverse Event Reporting and Follow-up: Patients will be assessed for adverse events daily during receipt of study therapy, and for 7 days following completion of study drug therapy, provided they remain hospitalized during this 7-day post-therapy period. In addition, patients will be contacted 30 days (±2 days) after receiving the last dose of study therapy, to assess their clinical status and any active adverse events at that time. This final assessment can be done virtually, by telephone or electronically (email) if the patient cannot be contacted by phone. No in-person visit is required.

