# 1.0 STUDY SYNOPSIS

This is an investigator initiated, open label trial of defibrotide for therapy of patients with SARS-CoV2 related acute respiratory distress syndrome (ARDS). The primary endpoint is safety and tolerability. Secondary endpoints will assess response and ventilator free survival.

*Eligibility*: Patients ≥ 18 years in age with evidence of SARS-CoV2 related ARDS. All patients must exhibit signs of coagulopathy evidenced by a D-dimer > 2X ULN.

**Study therapy:** Defibrotide will be administered intravenously (IV) every 6 hours (Q6H) for 7 days of therapy. Patients who meet defined toxicity and/or efficacy criteria within the 7-day period may cease study therapy at that earlier time point. Patients with a partial response to study therapy by day 7 (defined as > 20% decrease in supplemental oxygen) may continue to receive an additional 7 days of therapy (14 days total therapy). Toxicity (including rate of hemorrhage / bleeding) will be assessed. Each patient will be monitored for 14 days, including 7 days of therapy and 7 days of post-therapy observation.

**Sample Size:** 12 patients. An interim assessment for toxicity and early mortality will be performed after the first six patients have enrolled. Accrual may proceed to a maximum of 12 patients, if the stopping rules are not met within the first six patients.

**Other:** The study will target patients with either early or late-phase ARDS, provided patients have not required mechanical ventilation for > 7 consecutive days. The study allows co-enrollment with other SARS-CoV2 therapy trials, provided those trials are not also utilizing other anti-coagulant or fibrinolytic agents.

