# 8.1 Primary study endpoint

The primary safety endpoint will be the occurrence of major toxicity, specifically hemorrhagic complications within 14 days of initiation of treatment.

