# 10.2 Adverse Event Reporting Requirements

The descriptions and grading scales used in the revised NCI Common Terminology Criteria for Adverse Events (CTCAE) version 5.0 will be utilized for AE reporting. The CTCAE v5.0 mapping document can be downloaded at the CTEP website: https://ctep.cancer.gov/protocoldevelopment/electronic\_applications/docs/CTCAE\_v5\_Quick\_Reference\_5x7.pdf

Reporting requirements may include the following considerations: 1) the characteristics of the adverse event including the *grade* (severity); 2) the *relationship to the study therapy* (attribution); and 3) the *prior experience* (expectedness) of the adverse event.

Adverse events (AE) refer to any untoward medical occurrence associated with the use of an intervention in humans, whether or not considered intervention-related (21 CFR 312.32 (a)). By way of example and without limitation, an AE can be any unfavorable and unintended sign (for example, an abnormal laboratory finding), symptom, or disease temporally associated with the use of the Study Drug.

Protocol-defined and serious AE will collected for 30 days following receipt of the last DF dose, or death, whichever comes first. In addition, patients with drug related AE will be monitored until symptom resolution, even if the symptoms extend beyond the 30-day period.

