#### 10.6 Additional Protocol-Defined Serious Adverse Events

 Bleeding / Hemorrhage: The development of a bleeding diathesis that in the opinion of the treating physicians may be potentially life-threatening, including (but not limited to) pulmonary hemorrhage, CNS bleed / hemorrhage, gastro-intestinal hemorrhage (frank hematochezia or hematemesis), genito-urinary bleeding (gross hematuria), or uncontrolled epistaxis / oral mucosal bleeding as defined in section 6.4.

- Acute Renal Dysfunction: Abnormal kidney function requiring dialysis (including hemofiltration) in patients who did not require this procedure prior to study entry, or a rise in serum creatinine of greater than 3 times baseline for over 48 hours.
- Deterioration of Respiratory Status: Impairment of respiratory function requiring tracheostomy or the institution of high frequency oscillatory ventilation (HFOV) or ECMO, if not present at study entry. This excludes intubation for re-operation or temporary intubation for diagnostic or therapeutic procedures.
- Multi-System Organ Failure: The development of potentially reversible physiological derangement involving 2 or more organ systems not involved in the ARDS, provided this organ dysfunction was not present at the time of study entry.

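### The 14-day bleeding endpoint has no scheduled ascertainment through Day 14 in patients discharged before Day 14, or in inpatients who stop drug before Day 7

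*Combined protocol and SAP*

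**What the plan says.** Section 8.1 defines the primary safety endpoint as major toxicity, specifically "hemorrhagic complications within 14 days of initiation of treatment". Section 8.3 monitors major bleeding continually and suspends accrual at 3 events in the first 6 patients or 4 in the first 11.

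The schedule in Section 7.7 has no column between Day 7 and the contact 30 days after therapy. Note h sets daily adverse event assessment during therapy and for 7 days afterwards, "provided they remain hospitalized during this 7-day post-therapy period". The contact 30 (±2) days after the last dose is "to assess their clinical status and any active adverse events at that time". Note e expects some discharges before Day 14 and waives the Day 14 pulmonary indices for those patients. Section 7.0 ends study blood tests with the last day of drug.

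Two other places say more than note h:

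- Section 10.2: "Protocol-defined and serious AE will collected for 30 days following receipt of the last DF dose, or death, whichever comes first". There is no hospitalization condition. Section 10.6 includes bleeding among these events: "The development of a bleeding diathesis that in the opinion of the treating physicians may be potentially life-threatening".
- Synopsis: "Each patient will be monitored for 14 days, including 7 days of therapy and 7 days of post-therapy observation".

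On duration, Section 6.3 states: "The planned duration of study therapy is 7 days (168 hours) from study entry". It also allows responders to stop earlier and partial responders to continue to 14 days.

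**The concern.** The endpoint window is fixed at 14 days from the first dose. The assessment window is tied to the last dose and to hospital stay. The two coincide only for a 7-day course in a patient who stays in hospital to Day 14, or when therapy itself continues to Day 14.

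Under Section 8.5 anyone who receives one dose is evaluable, so a bleed that nobody elicits is counted as no bleed. In a trial of at most 12 patients whose purpose is bleeding safety, such errors all run one way: towards a lower estimate and a later or absent suspension. A bleed first learned of at the 30-day contact can still enter the final estimate. It reaches the monitoring rule weeks late, however, when more patients may have been enrolled. Day 14 vital status, which drives the mortality rule in Section 8.4, likewise has no scheduled check after discharge.

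**Working it through.** **1. Coverage of the 14-day window under note h**

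| Patient | Daily assessment ends | Scheduled cover from then to Day 14 | Next contact (last dose + 30 ± 2) |
|---|---|---|---|
| 7-day course, in hospital to Day 14 | Day 7 + 7 = Day 14 | complete | about Day 37 |
| 7-day course, discharged before Day 14 | day of discharge | none | about Day 37 |
| Stops at Day 4, still in hospital | Day 4 + 7 = Day 11 | none for Days 12–14 | about Day 34 |
| Therapy continued to Day 14 | beyond Day 14 | complete | about Day 44 |

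The gap therefore concerns the second and third rows.

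**2. The plan's own stopping figures (Section 8.3)**

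Inputs: suspend at ≥3 of 6 or ≥4 of 11; prior Beta(2,8); posterior threshold 0.80. The posterior probability that the rate exceeds 0.20 is 0.836 at 3/6 and 0.804 at 4/11, so the boundaries fit the rule.

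Counts never fall, so with X the bleeds in the first 6 patients and Y those in the next 5:

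P(suspend) = P(X≥3) + P(X=0)·P(Y≥4) + P(X=1)·P(Y≥3) + P(X=2)·P(Y≥2)

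- True rate 0.30: 0.2557 + (0.1176×0.0308 + 0.3025×0.1631 + 0.3241×0.4718) = 0.2557 + 0.2059 = 0.462
- True rate 0.40: 0.4557 + (0.0467×0.0870 + 0.1866×0.3174 + 0.3110×0.6630) = 0.4557 + 0.2695 = 0.725
- True rate 0.20, same formula: 0.188

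The plan states 0.19, 0.47 and 0.73 at true rates of 0.20, 0.30 and 0.40. All agree to within 0.01. These figures assume that every bleed is seen and seen at once.

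**3. Effect of missed bleeds**

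Let d be the share of patients discharged before Day 14. Let f be the share of their 14-day bleeds that occur after discharge and are missed. If bleeding risk does not depend on discharge, the missed share is m = d×f and the observed rate is p(1 − m). The documents give neither d nor f, so the values below are assumptions.

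| d = f | m | Observed rate at true 0.30 | P(suspend) | Observed rate at true 0.40 | P(suspend) |
|---|---|---|---|---|---|
| 0 | 0 | 0.300 | 0.462 | 0.400 | 0.725 |
| 10% | 1% | 0.297 | 0.453 | 0.396 | 0.716 |
| 25% | 6.25% | 0.281 | 0.407 | 0.375 | 0.666 |
| 50% | 25% | 0.225 | 0.250 | 0.300 | 0.462 |

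The last entry can be checked directly: 0.40×0.75 = 0.30, so it must equal the 0.462 found for a true rate of 0.30. The model treats bleeds as missed, not delayed. The effect of delay depends on accrual pace, which the documents do not give.

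**The case against.** A reader might infer that bleeding is followed only while the patient is in hospital. The documents do not support that. Section 10.2 collects protocol-defined and serious events for 30 days after the last dose wherever the patient is, and Section 10.6 brings potentially life-threatening bleeding under that heading. The stopping rule counts major bleeds, which Appendix 3 defines as fatal, in a critical site, or with a hemoglobin fall leading to transfusion of two or more units. Such events usually bring a patient back to care and would be recalled at 30 days. The 30-day contact also covers clinical status, so nothing tells staff to ignore a resolved bleed.

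Much of this stands. It makes a large loss of major bleeds less likely. It does not supply a procedure: Section 10.2 sets a period, not a method, and the reporting clock in Section 10.7 starts at first awareness, which is the step left open after discharge. The bleeding event in Section 10.6 also rests on the treating physicians' opinion and is not the Appendix 3 definition.

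A reader might also take a loss of 10% or 20% of all bleeds as the expected effect. At a true 40% rate that would cut suspension probability to 0.628 or 0.519. Nothing in the documents supports those shares; under the model above a 20% loss needs d and f of about 45% each (0.45×0.45 ≈ 0.20).

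Finally, a reader might infer that Day 14 ventilator-free survival is unknown in discharged patients. That is weak: on the scale in Appendix 1 ventilation is a hospitalized state, so what is needed is readmission and vital status.

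**Conclusion.** The point holds as one of scheduled ascertainment and of inconsistent text. If note h is followed as written, the primary endpoint is not actively ascertained through Day 14 in patients discharged before then, nor in inpatients who stop drug before Day 7. The synopsis and Section 10.2 commit to more than note h delivers and do not say how it is to be obtained after discharge.

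The direction is certain: missed bleeds can only lower the estimate and weaken the rule. The size is not. Over assumed shares of 10% to 50% for both d and f, the fall in suspension probability runs from negligible (0.725 to 0.716) to substantial (0.725 to 0.462) at a true 40% rate, and from 0.462 to between 0.453 and 0.250 at a true 30% rate. These figures assume that bleeding risk is unrelated to discharge; a lower risk in patients well enough to go home would make the loss smaller. The stopping-rule probabilities in Section 8.3 are sound for complete ascertainment and are not in question.

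**What to change.** 1. Add a Day 14 (±2 days) check of bleeding and vital status, by telephone or record review, for every treated patient not then under daily assessment, including inpatients whose 7-day post-therapy period has ended. It should cover the period up to Day 14 and also record readmission and ventilation.
2. Reword note h so that the 30-day contact asks for all bleeding and serious adverse events since the last contact, not only those still active. This also picks up any days left open by a check made before Day 14.
3. Reconcile note h with the synopsis and Section 10.2, so that all three state the same period, the same patients and the means of collection.

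The cost is at most 12 short calls or record checks, one entry in the schedule of events and a wording change. Sample size, stopping boundaries and treatment are unaffected.
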